#### Subgroup analyses

Subgroup analyses of OS will similarly be performed to determine whether the treatment effect is concordant among subgroups. To avoid possible issue related to small number of events, subgroup analyses will not be adjusted for the stratification factors used at randomization. Subgroups are defined in Section 7.9.

A forest plot displaying the HR for treatment comparison and 95% confidence interval will be presented by subgroup. The HR will be estimated by use of Cox proportional hazards models with treatment as covariate.

SAS PROC PHREG will be used for these subgroup analyses:

```
PROC PHREG DATA=ADTTE;
WHERE PARAMCD=&ENDPOINT;
CLASS TRTP(REF='PLACEBO + ADT') STRATUM1 STRATUM2;
MODEL AVAL*CNSR(1)= TREATMENT / RL TIES=DISCRETE;
BY SUBGROUP;
RUN;
```

## Sensitivity analyses

- To adjust the treatment crossover effect on OS, the following methods may be used.
  - Rank-Preserving Structural Failure Time Model (RPSFTM) [Robins and Tsiatis, 1991]). This method is to assess the impact of patients who switched placebo to enzalutamide by reconstructing the survival duration of placebo patients, as if they had never received enzalutamide.
- To assess potential impact of COVID-19, the following analyses may be conducted.
  - Same as OS primary analysis, except that patients died due to COVID-19 infection will be censored at the date of death.
  - Same as OS primary analysis, but exclude the subjects died due to COVID-19 infection from the analysis.
- To estimate the size of the treatment effect separately for 2 time periods, before and after the first 6 months from randomization, piecewise exponential model may be used to estimate the HR.

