## 3.2 Study Design

This is a multinational phase 3, randomized, double-blind, placebo-controlled efficacy and safety study of enzalutamide plus ADT versus placebo plus ADT in patients with mHSPC. After the double-blind period has completed, eligible patients were allowed to received open label enzalutamide in an open label extension period.

Approximately 1100 subjects were randomized centrally 1:1, and the randomization was stratified by volume of disease (low versus high) and prior docetaxel therapy for prostate cancer (no prior docetaxel, 1-5 cycles, 6 cycles). High volume of disease is defined as metastases involving the viscera or, in the absence of visceral lesions, there must be 4 or more bone lesions, at least 1 of which must be in a bony structure beyond the vertebral column and pelvic bone. Prior docetaxel therapy is defined as 1 or more cycles of docetaxel but no more than 6 cycles.

In this study, patients received 4 capsules of enzalutamide (40 mg each) or placebo per day orally in the double-blind period. After the double-blind period has completed, eligible patients received 4 capsules of enzalutamide (40 mg each) in the open label extension period. As long as the patient is tolerating the study drug, the treatment should be continued until radiographic disease progression (rPD) or starting an investigational agent or new therapy for treatment of prostate cancer. Patients who discontinue study drug without radiographic progression will continue to follow the radiographic assessment schedule until radiographic progression event or until the target number of deaths is reached for the final analysis of OS.

The following assessments of prostate cancer status will be collected during OLE: soft tissue disease on CT scan or on MRI, bone disease on radionuclide bone scans, survival status, EQ-5D-5L, QLQ-PR25, FACT-P for QoL and BPI-SF for pain symptom assessment. Throughout the study, safety and tolerability were assessed by the recording of adverse events (AE), vital signs, physical examinations, 12-lead electrocardiograms (ECG), and safety laboratory evaluations (including PSA).

Patients will have a safety follow-up visit 30 days after their last dose of study drug or prior to initiation of new antineoplastic therapy for prostate cancer, whichever occurs first. All

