## 4 SAMPLE SIZE

For OS, 342 death events will be required to provide 80% power to detect a target HR of 0.73 with a target difference in Kaplan-Meier estimated median of approximately 15 months (40 months for placebo versus 55 months for enzalutamide) at the 4% significance level under the assumption of an exponential distribution. This significance level was chosen to apply a parallel testing strategy between OS and other key secondary endpoints (with allocated type I error rate of 1%) as described in section 7.4.1.

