## 5 ANALYSIS SETS

#### 5.1 Intent-to-Treat Population

The Intent-to-Treat (ITT) population is defined as all subjects who were randomized in this study. The ITT population will be analyzed by treatment arm as randomized, (i.e., treatment arm by randomization assignment) regardless of whether or not study drug was administered. The ITT population will be used to conduct efficacy analyses, unless otherwise specified.

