#### 6.1 Overall Survival

OS is defined as the time from randomization to death from any cause. All deaths on or before the data cut-off will be included.

For patients who are alive at the time of the cut-off date, OS time will be censored on the last date the patient is known to be alive or the cut-off date, whichever occurs first. The date the patient is last known alive by the cut-off date will be derived as follows:

- for patients on treatment by the cut-off date (i.e., patients who did not discontinue from treatment), the date last known alive will be the cut-off date.
- for patients who withdraw consent by the cut-off date, the date last known alive is the date of consent withdrawal.
- for patients lost to follow up, the date last known alive depends on the period the patient was lost to follow-up. It will be as follows:

Period lost to follow-up	The date last known alive		
Since randomization (i.e. without	The date of randomization		
further post-randomization visit)			
During treatment period	The last assessment/visit date or the date of the last		
	dose of study drug, whichever occurs later		
Safety follow-up period	The date of the last dose of study drug or the last		
	treatment visit date collected on the End of Treatment		
	Case Report Form (CRF) page, whichever occurs last.		
Long-term follow-up period	The last visit/contact date (collected either on the		
	30 Day Follow-Up Status CRF page, or the Patient		
	Status - Survival CRF page or the Long-Term Follow-		
	Up Status CRF page).		

• for other patients (i.e., not on treatment, not withdrawn and not lost to follow-up) who are alive by the cut-off date, the date last known alive is the date of last visit (collected either on the Patient Status - Survival CRF page or the Long-Term Follow-Up Status CRF page) or the date of randomization, whichever occurs last.

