#### Figure 1 Testing Strategy for the Primary and Six Selected Secondary Endpoints

rPFS: radiographic progression-free survival; OS: overall survival; TTPP: time to PSA progression; TTNAnti: time to initiation of a new antineoplastic therapy; PSADecR: rate of PSA decline to <0.2 ng/mL; ORR: objective response rate; TTUri: the time to deterioration in urinary symptoms from the QLQ-PR25 \*OS will be tested at 0.05 only, if all other 5 secondary endpoints analyses are statistically significant at 0.01.

As the analysis for time to deterioration in urinary symptoms from the QLQ-PR25 was not significant, the final analysis of OS will be conducted at the level of significance of 0.04 (2-sided). The effect of Enzalutamide+ADT compared to placebo+ADT will be tested using a log-rank test stratified by prior docetaxel use (yes versus no) and disease volume (low versus high).

The null and alternative hypotheses to be tested are as follows:

The null hypothesis: OS for Placebo+ADT and Enzalutamide+ADT are not different The alternative hypothesis: OS for Placebo+ADT and Enzalutamide+ADT are different

The following SAS code will be used to compute the Kaplan-Meier estimates and curves, and the stratified log-rank test:

PROC LIFETEST DATA=INPUT ATRISK

```
PLOTS=SURVIVAL(CB)
OUTSURV=SURVPL
ALPHA=0.04
ALPHAQT=0.04 METHOD=KM;
TIME AVAL*CNSR(1);
STRATA STRATUM/ GROUP=TREATMENT;
RUN;
where INPUT is the input dataset
```

AVAL is the time to the event variable,

CNSR is 0 (patients with events) or 1 (patients without no event, i.e. patient censored) STRATUM is the stratification variable (volume of disease and prior docetaxel use) TREATMENT is the treatment variable

Kaplan-Meier methods will be used to estimate the distribution of OS events by treatment group. The median OS will be estimated using the corresponding 50th percentile of Kaplan-Meier estimates. A two-sided 95% confidence interval will be provided for this estimate by use of the Brookmeyer and Crowley method. The 25th percentile and the 75th percentile of OS will also be provided. A Kaplan-Meier plot by treatment group will be presented. The estimates of the event free rate on a 3-monthly basis up to 1 year and every 6 months thereafter will be summarized by treatment group, as long as at least 10 patients are at risk.

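### The optional OS sensitivity analysis that drops subjects who died of COVID-19 selects on the outcome and biases the HR, slightly, against the arm with more such deaths

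*SAP*

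**What the plan says.** Under Sensitivity analyses in SAP 7.4.1, two analyses are offered to gauge the effect of COVID-19 on OS. Both are optional. The first repeats the primary OS analysis with COVID-19 deaths censored at the date of death. The second repeats it but would "exclude the subjects died due to COVID-19 infection from the analysis". The SAP gives no reason for the second and does not say how to read the pair if they disagree.

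The primary analysis is defined elsewhere in the SAP. Section 6.1: "OS is defined as the time from randomization to death from any cause". Section 5.1, after defining the ITT set as all randomized subjects: "The ITT population will be used to conduct efficacy analyses, unless otherwise specified". Section 7.4.1 tests OS with a stratified log-rank test at two-sided 0.04, and also has the primary cause of death summarized and listed. Section 4 gives the event target: "342 death events will be required to provide 80% power to detect a target HR of 0.73".

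**The concern.** A subject who dies of COVID-19 at month 30 was under observation and free of any other fatal event for 30 months. Censoring at month 30 keeps that time in the risk sets. Excluding the subject removes it, and the only reason is something that happened at the end of it. Another subject with the same 30 months and no COVID-19 death stays in. The arm that loses more subjects this way loses more event-free time but none of its other deaths, so its hazard of other death is overstated.

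With equal losses the two overstatements cancel in the HR. With unequal losses they do not, and an imbalance in COVID-19 deaths is exactly what would lead someone to consult this analysis. At stake is the reading of a robustness check: a difference between the excluded and primary HRs would mix the effect of COVID-19 with a distortion that the exclusion creates.

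**Working it through.** **Inputs from the documents.** SAP 4: 342 deaths, 80% power, HR 0.73, medians of "40 months for placebo versus 55 months for enzalutamide", "under the assumption of an exponential distribution", 4% level. SAP 7.4.1: the level is two-sided. SAP 3.2: "Approximately 1100 subjects were randomized centrally 1:1", so about 550 per arm.

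**Assumptions not in the documents.** 0 to 20 COVID-19 deaths per arm; uniform accrual over 22 months; COVID-19 deaths only in the last 14 months before cut-off; COVID-19 death independent of other death within arm; unstratified Cox model.

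**Step 1: the plan's own figure.** Schoenfeld: 4(2.054 + 0.842)² / (ln 0.73)² = 339 deaths. Freedman: (2.054 + 0.842)² × (1.73/0.27)² = 345. Power at 342 deaths is 80.4%. The 342 reproduces. The standard error of the log HR is about 2/√342 = 0.108.

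**Step 2: simulation with a fixed true HR.** Four million subjects per scenario, with counts scaled to 1100 subjects and about 342 deaths. Other deaths are exponential, with a placebo median of 40 months and a true HR of 0.73.

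| COVID-19 deaths, enzalutamide / placebo | HR, all deaths | HR, censored | HR, excluded | Excluded ÷ censored |
|---|---|---|---|---|
| 5 / 5 | 0.735 | 0.730 | 0.730 | 0.9998 |
| 10 / 10 | 0.737 | 0.728 | 0.727 | 0.9989 |
| 10 / 5 | 0.758 | 0.729 | 0.734 | 1.0067 |
| 5 / 10 | 0.718 | 0.730 | 0.725 | 0.9930 |
| 15 / 5 | 0.784 | 0.727 | 0.738 | 1.0150 |
| 5 / 15 | 0.696 | 0.730 | 0.718 | 0.9842 |
| 20 / 0 | 0.837 | 0.731 | 0.754 | 1.0303 |
| 0 / 20 | 0.657 | 0.732 | 0.709 | 0.9694 |

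Censoring recovers 0.73 to within simulation error. Exclusion moves away from it, always against the arm with more COVID-19 deaths. With a true HR of 1.0, exclusion gives 1.030 at 20 / 0 and 0.971 at 0 / 20.

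**Step 3: hand check of the mechanism at 20 / 0.** The cut-off in that run was 34.7 months after the start of accrual.
- Mean potential follow-up: 34.7 − 11 = 23.7 months.
- Enzalutamide hazard: 0.73 × ln 2 / 40 = 0.01265 per month.
- Expected time at risk: about (1 − e^(−0.01265 × 23.7)) / 0.01265 = 20.5 months, or 550 × 20.5 = 11,275 subject-months in the arm.
- Mean follow-up of a COVID-19 death, taken at the middle of the 14-month window: about 34.7 − 7 − 11 = 16.7 months. Twenty of them carry 334 subject-months.
- Deleting these inflates the arm's hazard by 11,275 / (11,275 − 334) = 1.031, against 1.0303 in the simulation.

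The bias is therefore essentially the share of the arm's person-time that is deleted.

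**Step 4: a second design.** 400 trials per scenario, 342 deaths of which 16 are assigned to COVID-19, medians 40 and 55 months, 22-month accrual, COVID-19 deaths from the last 16 months. HR censored → excluded, with deaths given as enzalutamide / placebo:
- 8 / 8: 0.7192 → 0.7191
- 12 / 4: 0.6826 → 0.6904 (ratio 1.011)
- 4 / 12: 0.7559 → 0.7468 (0.988)
- 16 / 0: 0.6529 → 0.6683 (1.024)
- 0 / 16: 0.7929 → 0.7742 (0.976)

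Here the COVID-19 deaths are taken out of a fixed 342, so the HR for the remaining deaths changes between scenarios. This design measures only the gap between the two analyses. Bias against a known value comes from step 2.

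**The case against.** The strongest reply is that nothing depends on this analysis. It is optional and carries no alpha, and the sounder censoring version stands directly above it. Section 5.1 allows analyses outside the ITT set when specified. The cause-of-death summary should reveal any imbalance, provided COVID-19 deaths are recorded as such. All of this stands and limits the weight of the point. It does not make the exclusion valid: permission to use another set does not cure selection on an outcome after randomization.

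A second reply is that large imbalance is unlikely. If 16 deaths fell on either arm with equal chance, a split at least as uneven as 12 vs 4 has two-sided probability 0.077, and 16 vs 0 has 0.00003. That also stands, so the 2 to 3% figures are bounds, not expectations. On the log scale, the shift is ln(1.0150) / 0.108 = 0.14 standard errors at 15 / 5 and ln(1.0303) / 0.108 = 0.28 at 20 / 0.

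A third reply is that censoring has its own assumption. It gives the HR that would hold without COVID-19 only if COVID-19 death is non-informative for other death, and frailty could link the two. This is correct and belongs in the fix. The simulation builds in independence, so it cannot show that censoring is free of bias in practice.

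**Conclusion.** The point holds as a minor one. The exclusion analysis conditions on the outcome and deletes valid follow-up, and it adds nothing that the censoring analysis does not already provide. Under the stated assumptions the HR bias is about 0% when COVID-19 deaths are balanced, about 1 to 1.5% at moderate imbalance and about 2 to 3% at the extreme. All counts are assumed. The size also depends on timing, because deaths after longer follow-up delete more person-time. If 20 COVID-19 deaths carried the arm's average follow-up, the deleted share would be 20/550 = 3.6%.

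A reader might infer that the SAP abandons ITT for OS, or that the confirmatory OS result is at risk. The documents do not support that: the primary test counts death from any cause in all randomized subjects at two-sided 0.04, and the 342-death target is unchanged. A reader might also infer that the exclusion would materially mislead. At a small fraction of a standard error, that is not shown.

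**What to change.** Delete the exclusion bullet from SAP 7.4.1. If it is kept, label it descriptive and not for interpretation.

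Keep the analysis that censors at COVID-19 death, run it in the full ITT set, and describe its result as a cause-specific HR. Add one sentence stating that reading it as the effect in the absence of COVID-19 assumes non-informative censoring. Report COVID-19 deaths by arm beside it. If a second view is wanted, cumulative incidence with COVID-19 death as a competing event keeps every randomized subject; this is optional.

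The cost is one bullet removed, one sentence added and one line in the cause-of-death table already planned. No new data and no change to the event target or alpha are needed. SAP 1 allows revision before database hard lock.

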#### 7.4.2 Time to Initiation of a New Antineoplastic Therapy

This will be analyzed using the same analysis methods as OS, but formal statistical test will not be conducted.

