### 7.4.2 Analysis of Secondary Endpoints

All secondary endpoint analyses will be performed at the time of the rPFS final analysis.

The following 6 secondary endpoints will be tested: OS, time to PSA progression (TTPSA), time to initiation of a new antineoplastic therapy (TTNAnti), the rate of PSA decline to < 0.2ng/mL (PSADecR), the objective response rate (ORR) and time to deterioration in urinary symptoms (TTUri). A parallel testing strategy between OS (with allocated type I error rate 0.04) and the other 5 endpoints (with allocated type I error rate 0.01) will be performed, as summarized in Figure 2.

- CONFIDENTIAL -

Figure 2 Testing Strategy for the Primary and 6 Selected Secondary Endpoints

OS: overall survival; ORR: objective response rate; PSADecR: rate of PSA decline to < 0.2 ng/mL; rPFS: radiographic progression-free survival; TTNAnti: time to initiation of a new antineoplastic therapy; TTPSA: time to PSA progression; TTUri: time to deterioration in urinary symptoms from the QLQ-PR25. \*OS will be tested at 0.05 only if the other 5 secondary endpoints analyses are statistically significant at 0.01.

Details of the primary and the selected secondary endpoints testing as a step-by-step approach will be described in the Statistical Analysis Plan (SAP).

One interim analysis and a final analysis are planned for OS. The interim analysis of OS will be performed at the time of the rPFS final analysis. If this interim analysis of OS is statistically significant, it will be reported as the final analysis and no subsequent analysis will be performed. At the time of the planned final analysis of OS, no additional analyses of other efficacy endpoints will be conducted.

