#### 12.6.7 Statistical Methods

Subject disposition data (patients who continued to the open-label extension and primary reasons for treatment discontinuation and study discontinuation) will be summarized descriptively by study periods, in the ITT population for the blind study period and on patients who started open-label enzalutamide for the open-label extension.

Data collected in the open-label extension will only be summarized by descriptive statistics unless otherwise specified. Descriptive statistics will include number of subjects, mean, standard deviation, minimum, median and maximum for continuous endpoints, and frequency and percentage for categorical endpoints.

An open-label extension data summary will be presented for subjects who switched treatment from placebo+ADT to enzalutamide+ADT (i.e., subjects who received placebo+ADT during the blinded period). A combined double-blind and open-label data summary on

enzalutamide+ADT will be presented for all subjects who received enzalutamide+ADT either during the blind period or the open-label extension (i.e., overall).

Enzalutamide exposure will be summarized and listed in the open-label extension and in the combined double-blind and open-label, as appropriate.

Adverse events will be coded using MedDRA. The number and percentage of AEs, SAEs, AEs leading to discontinuation and AEs related to study drug will be summarized by system organ class and preferred term. The number and percentage of AEs by severity (reported according to NCI-CTCAE version 4.03) will also be summarized. All AEs will be listed.

For quantitative laboratory measurements and vital signs, descriptive statistics will be used to summarize results and change from baseline by visit. Baseline will be defined as the latest value recorded prior to the first enzalutamide administration. Using the NCI-CTCAE version 4.03, laboratory values will be classified as Grade 1 through 4, where possible. Laboratory and vital sign data will be displayed in listings.

A final OS analysis will be conducted after approximately 342 deaths are observed.

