## **1 INTRODUCTION**

A Statistical Analysis Plan (SAP) contains a more technical and detailed elaboration of the principal features of the analysis described in the protocol and includes detailed procedures for executing the statistical analysis of the primary and secondary endpoints and other data. This SAP contains details related to analyses specific to the Open Label Extension Period (OLE), in addition to the SAP (version 3.0) used for the primary analysis.

The SAP is finalized and signed prior to database hard lock to ensure lack of bias. If needed, revisions to the approved SAP may be made prior to database hard lock. Revisions will be version controlled.

This statistical analysis is coordinated by the responsible biostatistician of Astellas Pharma. Any changes from the analyses planned in the SAP will be justified in the Clinical Study Report.

Prior to database hard lock, a final blinded review of data and TLFs meeting will be held to allow a review of the clinical trial data and to verify the data that will be used for any new analysis set classification. If required, consequences for the statistical analysis will be discussed and documented. A meeting to determine analysis set classifications may also be held prior to database hard lock.

This SAP for the open-label extension is a supplement to the main study SAP which was completed prior to unblinding the study. The methods for the analysis of overall survival were established in the main study SAP. This SAP includes those methods and adds sensitivity and subgroup analyses for overall survival and an updated analysis for time to new antineoplastic. This SAP also describes the planned summaries for safety, disposition, and other data to incorporate the placebo patients who crossed over to open-label enzalutamide.

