#### 7.4.1 Overall Survival

At the time of the primary analysis of rPFS, the interim analysis of OS was not significant (84 deaths from any cause, 39 in Enzalutamide + ADT group and 45 in Placebo + ADT group, p=0.3361 from stratified log-rank test). The final analysis of OS will be conducted when approximately 342 events (death from any cause) have occurred.

At the time of the primary analysis of rPFS, the following six key secondary endpoints were tested: OS, Time to PSA progression, time to initiation of a new antineoplastic therapy, the rate of PSA decline to <0.2ng/mL (PSADecR), objective response rate and the time to deterioration in urinary symptoms from the QLQ-PR25. To maintain the family-wise 2-sided type I error rate at 0.05, a parallel testing strategy between OS (with allocated type I error rate 0.04) and the other five endpoints (with allocated type I error rate 0.01) was performed, as summarized in Figure 1.

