The benefit of Enzalutamide+ADT compared to placebo+ADT will be summarized by a single HR with its 95% CI based on a Cox regression model stratified for the prior docetaxel use and disease volume. The null and alternative hypotheses regarding OS can be rephrased in terms of the HR,  $\lambda_{ArmA} / \lambda_{ArmB}$ , where  $\lambda_{ArmA}$  represents the hazard of OS for Enzalutamide+ADT and  $\lambda_{ArmB}$  represents the hazard of OS for placebo+ADT. A HR of < 1 indicates that the OS is prolonged for patients randomized to Enzalutamide+ADT compared with patients randomized to placebo+ADT. The null and alternative hypotheses, respectively, can be written as follows:

$$H_0: \frac{\lambda_{ArmA}}{\lambda_{ArmB}} = 1 \qquad H_1: \frac{\lambda_{ArmA}}{\lambda_{ArmB}} \neq 1$$

The estimated HR of Enzalutamide+ADT to placebo+ADT,  $\lambda_{ArmA} / \lambda_{ArmB}$ , and its 95% confidence interval will be provided.

SAS PROC PHREG will be used for the analysis with the "DISCRETE" option for tie breaker as follows:

```
PROC PHREG DATA=ADTTE;
WHERE PARAMCD=&ENDPOINT;
CLASS TRTP(REF='PLACEBO + ADT') STRATUM1 STRATUM2;
MODEL AVAL*CNSR(1)= TREATMENT / RL TIES=DISCRETE;
STRATA STRATUM1 STRATUM2;
RUN;
```

```
where INPUT is the input dataset
```

AVAL is the time to the event variable,

CNRS is 1 (patients with no events) or 0 ( patients with events) STRATUM are the stratification variables (volume of disease and prior docetaxel use) TREATMENT is the treatment variable

If the estimate of the HR  $\lambda_{ArmA} / \lambda_{ArmB} < 1$  and the results from the log-rank test lead to the rejection of H0 in favor of HA, then it will be concluded that Enzalutamide+ADT prolongs OS compared to placebo+ADT.

The primary cause of death will be summarized and listed.

The median follow-up time on study will be calculated as the 50th percentile of Kaplan-Meier estimates from the OS time analysis when reverting the censoring (flag).

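### Must the SAP's update of time to new antineoplastic therapy at the final OS analysis change because Protocol 7.4.2 rules out such analyses?

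*SAP*

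**What the plan says.** Protocol 7.4.2 fixes the timing of the secondary endpoints: "All secondary endpoint analyses will be performed at the time of the rPFS final analysis". For the later survival analysis it adds: "At the time of the planned final analysis of OS, no additional analyses of other efficacy endpoints will be conducted". Protocol 12.6.7, on the open-label extension, says: "Data collected in the open-label extension will only be summarized by descriptive statistics unless otherwise specified". The statistics it then lists are simple summaries, and the only efficacy analysis it names is OS.

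The SAP of 18 July 2021 supplements the main study SAP and covers the extension and the final OS analysis. Its introduction says that it "adds sensitivity and subgroup analyses for overall survival and an updated analysis for time to new antineoplastic". SAP 3.1 gives this update a descriptive role in support of OS. SAP 7.4.2 sets the method: "This will be analyzed using the same analysis methods as OS, but formal statistical test will not be conducted". The OS methods in SAP 7.4.1 are Kaplan-Meier estimates and a treatment effect "summarized by a single HR with its 95% CI based on a Cox regression model", stratified by prior docetaxel use and disease volume.

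SAP 7.4.1 also records the history of the endpoint. It belongs to the group introduced by "At the time of the primary analysis of rPFS, the following six key secondary endpoints were tested". The outcome of that testing set the OS level at 0.04: "As the analysis for time to deterioration in urinary symptoms from the QLQ-PR25 was not significant".

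**The concern.** Read literally, the two documents cannot both be followed. A report written to the SAP will contain a second hazard ratio for an endpoint that has already been tested, and a report written to the protocol will not. The SAP was written with the first results known, and Protocol 1.4 already reports improvement on this endpoint. A further estimate added at that stage invites the question whether it was chosen for its result.

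The second hazard ratio is also not like-for-like with the first. Placebo patients could switch to enzalutamide in the extension, and SAP 6.2 and 7.4.2 do not say how that time is handled. If the switch counted as a new therapy, it would add placebo-arm events. If it does not, open-label enzalutamide time sits in the placebo arm. At stake would be the status and meaning of a published estimate.

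**Working it through.** **1. What the update is tied to.** The plan has no figure of its own for this endpoint. The update accompanies the final OS analysis at about 342 deaths, so that is the figure to reproduce. Inputs (Protocol 7.1, SAP 4 and 7.4.1): HR 0.73, 80% power, two-sided level 0.04, 1:1 allocation.

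- Schoenfeld: d = 4(z₀.₉₈ + z₀.₈₀)² / (ln HR)² = 4(2.054 + 0.842)² / (0.3147)² = 4 × 8.383 / 0.0990, which gives 339.
- Freedman: d = (z₀.₉₈ + z₀.₈₀)² × [(1 + HR)/(1 − HR)]² = 8.383 × (1.73/0.27)², which gives 345.
- Power at 342 deaths: Φ(½ × √342 × 0.3147 − 2.054) = Φ(0.856) = 0.804.

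The stated 342 lies between the two formulas. Nothing in it depends on time to new therapy.

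**2. Error control.** OS has 0.04 and the other five key secondary endpoints share 0.01; 0.04 + 0.01 = 0.05. All six were tested at the rPFS analysis. The updated analysis makes no test, so the sum is unchanged.

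**3. Extent of the mismatch.** Protocol 2.3.2 lists 10 secondary endpoints, 9 without OS. At the final OS analysis the protocol allows 0 of the 9 to be re-analysed, and the SAP re-analyses 1.

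**4. Is the hazard ratio's meaning open?** Setting the relevant sections side by side:

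| Place | What it settles |
|---|---|
| SAP 5.1 and 7.4 | Efficacy is analysed in the ITT population, by randomised arm, unless stated otherwise |
| SAP 7.4.1, inherited by 7.4.2 | The hazard ratio compares patients by the arm to which they were randomised |
| SAP 6.2 | Time starts at randomisation; events come from the new prostate cancer therapy CRF pages, for therapy that follows study drug |
| SAP 6.3 | For the placebo group, starting open-label enzalutamide and starting a new antineoplastic therapy are listed as separate occurrences |
| SAP 7.2.4 | The table of first new therapy counts from the end of study drug, including enzalutamide taken in the extension |
| Protocol 12.6.6 | Starting a new prostate cancer therapy is a reason to stop open-label enzalutamide, so the latter cannot itself be that therapy |

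Together these give one reading. The switch is neither an event nor a censoring point, and the estimate is as randomised.

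**5. Direction of any crossover effect.** If enzalutamide started late still delays the next therapy, placebo patients who switch have later events, and the as-randomised hazard ratio moves towards 1. If it does nothing late, the ratio is unaffected. Neither case flatters enzalutamide. A size would need accrual, switch rates, cut-off times and a late treatment effect for this endpoint. The two documents do not supply them, so none is offered.

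**The case for a change.** The best case for a change runs as follows. The sentence in Protocol 7.4.2 has no exception for descriptive or untested work. Protocol 12.6.7 does not rescue the update, because a between-arm Cox hazard ratio is not among the statistics it lists. Protocol version 5.1, dated 18 April 2022, is later than the SAP and keeps the sentence. Both documents promise that the study report will justify changes from the SAP, so an analysis that follows the SAP but departs from the protocol triggers no disclosure. On crossover, one definition in SAP 7.2.4 speaks of doses after the last dose of enzalutamide or placebo, which could make a placebo patient's switch look like new therapy. A placebo patient who starts commercial enzalutamide has an event, while one who starts it in the extension has none.

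The first and second points stand, and so does the gap in the disclosure promise. The version dates carry little weight: version 5.1 is a nonsubstantial amendment made to extend the study period, so its date does not show that the sentence was reconsidered. The phrase in SAP 7.2.4 belongs to a medication summary and would have to override the endpoint definition in SAP 6.2. The different treatment of commercial and extension enzalutamide follows from defining the event as therapy after study drug. SAP 6 also refers to the primary-analysis SAP for variable definitions. That document is not available here, so silence can be claimed only for this supplement.

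**Conclusion.** The mismatch between Protocol 7.4.2 and SAP 1 and 7.4.2 is genuine but clerical in effect. It concerns one untested, supportive summary out of nine secondary endpoints other than OS. It leaves the tested result for this endpoint, the OS level of 0.04 and every decision rule where they were. The crossover question is a gap that an analyst fills sensibly from the ITT rule, the event definition and the SAP's own separation of open-label enzalutamide from new therapy.

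Rewording either document would change no result. The one option that would change conduct is to drop the update. That would cost the information on subsequent treatment that SAP 3.1 wants beside OS, in a trial where placebo patients could cross over. Keeping it is a fair trade-off. The study report can present the update as descriptive and later than the tested analysis without any change to the plan.

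This conclusion assumes that the update is reported as the SAP labels it, with no test and in support of OS, and that extension enzalutamide is recorded as study drug and not on the new-therapy pages. If the updated hazard ratio were put forward as the endpoint's main result, the conclusion would not hold.
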